4.7.1.3 Visits in detail

	T1 Base- line	T2 ¹ OD, interve ntion time	T3 POD 1	T4 POD 2	T5 POD 3	T6 Dis- charge	T7 Follow- up ²
Inclusion and exclusion criteria	X						
Randomization	Х						
Demographic Data (age, gender, BMI)	Х						
Medical history(preexisting condition, premedication)	Х						
Operation data (type of surgery, CPB time, X-clamp time, transfusion)	X						
Respiratory parameter	Χ	Χ					
Hemodynamic parameters (MAP, HR, CVP, CI, CO)		X					
Laboratory parameter (lactate, hemoglobin, electrolytes)	X	X	Х	X	Х		
Renal parameter (BUN, creatinine, GFR, urine volume [ml/h], urinary output, fluid balance)	Х	X	X	Х	X	X	Х
Blood and urine samples	X	X					
AKI (severity, diagnosis by,		Χ	Х	Χ	Χ		

¹ After randomization to end of intervention (12h)

² d30, d60, d90

Date: 16.02.2017 Version: V1

CONFIDENTIA

transient/persistent, RRT dependency, RRT days)						
Scores (APACHE II, SOFA)	Х	Х	Х	Х		
Concomitant medication (vasopressors, radio contrast agents, diuretics, ACEi, ARBs)	Х	Х	Х	Х		
Renal recovery					Х	Х
Mortality						Х
Length of ICU and hospital stay						Х
Renal replacement therapy	Х	Х	Х	Х	Х	Х
MAKE						Х
Complications (myocardial infarction, cerebral ischemia, ICB, bleeding >300ml/hour, re-operation)	Х	Х	Х	Х	Х	Х

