	Severity of AKI (according to the KDIGO guidelines)					
	 Renal recovery at days 30, 60 and 90 (renal recovery is defined as serum creatinine levels < 0.5 mg/dl higher than baseline serum creatinine) 					
	30-day, 60-day and 90-day mortality					
	Length of ICU stay					
	Length of hospital stay					
	Need and duration of renal replacement therapy					
	• RRT at days 30, 60, 90					
	 MAKE₃₀, MAKE₆₀ and MAKE₉₀ (major adverse kidney events consisting of mortality, dialysis dependency, persistent renal dysfunction (defined as serum creatinine ≥ 2x compared to baseline value) 					
	Determination of different biomarkers					
	 Assessment of safety: complications in particular those related to the implementation of the KDIGO guidelines will be 					
	documented. No side effects have been reported.					
Number of subjects	To be assessed for eligibility: n=1000					
	To be allocated to the trial: n=310					
	To be analyzed: n=280 (140/ treatment arm)					
Time plan	First patient first visit (FPFV): 01/06/2017					
	Last patients first visit (LPFV): 31/05/2018					
	Last patient last visit (LPLV): 01/08/2018					
	Final study report: 01/11/2018					
	7 mai stady roport. 01/11/2010					

CONFIDENTIAL

Date: 16.02.2017 Version: V1

Statistics	Power analysis
	The required sample size is n=280 patients in total. This sample size is
	determined as follows:
	Patients will be randomized in a 1:1 ratio to one of the two treatment
	arms (intervention versus control). Randomization serves to estimate the
	incidence of AKI as secondary outcome to generate pre-information in
	terms of a pilot study for an upcoming confirmatory trial.
	The primary endpoint of the PrevAKI-multicenter trial is the compliance
	rate (Primary outcome: KDIGO recommendations fulfilled at all time), i.e.
	the proportion of patients who are treated according to the trial protocol.
	In order to estimate the compliance rate, the two treatment groups will
	be pooled together. In the primary analysis the compliance rate across
	all study patients will be estimated along with a two-sided 95%
	confidence interval (CI).
	As the compliance rate cannot be quantified in advance, we pursue a
	worst case approach and assume a compliance rate of 50%. In this case
	the CI has maximal width. Based on this assumption, with a sample size
	of n=280 patients the calculated 95% CI according to Clopper-Pearson
	(Fleiss 2003) ranges from 44% to 56%. Therefore, in case of any

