Acute kidney injury (AKI) is a well-recognized complication after cardiac surgery with an important impact on short- and long-term morbidity and mortality. Cardiopulmonary bypass (CPB) is employed in most cardiac surgical procedures. Despite numerous clinical trials testingdifferentpharmacologicaltreatments, a mean to prevent cardiac-surgery associated AKI (CSA-AKI) remains elusive. In 2012, the Kidney Disease: Improving Global Outcomes (KDIGO) workgroup published the KDIGO guidelines which recommend to implement a bundle of supportive measures in patients at high risk for AKI to prevent the development of AKI (discontinuationofall nephrotoxic agents when possible, optimization of volume status and hemodynamic parameters, discontinuation of angiotensin converting enzyme inhibitors (ACEi) and angiotensin receptor blockers (ARB) in the perioperative period to avoid severe hypotension, consideration of functional hemodynamic monitoring, close monitoring of serum creatinine and urine output, avoidance of hyperglycemia, consideration of alternatives to radiocontrast procedures). However, there is no evidence thatthis bundle of supportive measures actually prevents AKI.

Primary efficacy endpoint:

The primary endpoint is the compliance rate (proportion of patients treated according to the trial protocol):KDIGO recommendations fulfilled at all time

Secondary endpoint(s):

Occurrence of AKI within the first 72 hours after cardiac surgery (AKI is defined according to the KDIGO guidelines(1)); moderate and severe AKI (according to the KDIGO classification); severity of AKI; renal recovery at days 30, 60 and 90 (renal recovery is defined as serum creatinine levels < 0.5 mg/dl higher than baseline serum creatinine); 30-day, 60-day and 90-day mortality; length of ICU stay; length of hospital stay;need and duration of RRT; RRT at days 30, 60 and 90; MAKE₃₀, MAKE₆₀ and MAKE₉₀ (major adverse kidney events consisting of mortality, dialysis dependency persistent renal dysfunction (defined as serum creatinine ≥ 2x compared to baseline value).

Assessment of safety:

No side effects are expected by implementing the KDIGO guidelines.

CONFIDENTIAL

Date: 16.02.2017 Version: V1

2 Background and significance

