ACEi and ARBs are used to treat hypertension. A lot of patients undergoing cardiac surgery are on ACEi or ARBs which may cause severe and prolonged hypotension during anesthesia. These hypotensive episodes may lead to a reduced renal perfusion. Walsh et al. performed a cohort study on 33.330 patients undergoing non-cardiac surgery and demonstrated that intraoperative hypotensive episodes of less than 5 minutes with a MAP < 55 mmHg were associated with a significantly increased AKI rate (17). These datasupport the recommendation to discontinue ACEi and ARBs in the perioperative period and to consider functional hemodynamic monitoring to prevent the development of AKI.

Close monitoring of the classic biomarkers serumcreatinine and urinary output are important to detect functional damage early. The recommendation to avoid hyperglycemia stems from the landmark study by Van den Berghe et al. who showed a significant reduction of AKI in patients receiving strict glucose control(18). However, there are several trials showing that strict glucose control might not only be associated with higher AKI incidence but also with higher mortality rates(19, 20).

The severity of AKI is determined byvarious classification systems (RIFLE, AKIN, KDIGO) based on the degree of reduction of urinary output and/or increase of serum creatinine compared to baseline(1, 21). Both "classic biomarkers" are not appropriate for the detection of kidney damage without a loss of function, because both are functional markers. Urinary output is influenced by the use of diuretics and fluid status (e.g. hypervolemia) and has a low specificity. Serum-creatinine elevations are not detectable until 50% of the glomerular filtration rate (GFR) is lost, showing that this parameter has a low sensitivity. However, the injury occurs at a much earlier timepoint. New biomarkers such as [TIMP-2]*[IGFBP7] are injury markers which indicate tubular injury before loss of kidney functionoccurs(22). We performed an observational trial demonstrating that urinary [TIMP-2]*[IGFBP7] levels 4h after cardiac surgery showed a good performance to predict AKIwithin the next 72h (NC 0.3: sensitivity 0.80, specificity 0.83, PPV

CONFIDENTIAL

Date: 16.02.2017 Version: V1

0.80, NPV 0.83)(23). In those patients with AKI, biomarker elevations were apparent two days before the increase of serum-creatinine.

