4.2 Discussion of trial design

All patients will receive standard perioperative care. In the validation group, patients will be strictly treated according to the KDIGO guidelines and according to a special algorithm to optimize

CONFIDENTIAL

Date: 16.02.2017 Version: V1

volume status and hemodynamic parameters. The KDIGO recommendations are safe and have no side effects. In the control group, patients will receive standard care.

AKI after cardiac surgery is associated with an increased morbidity and mortality. Numerous clinical trials tested differentpharmacologicaltreatments,however no agents have been demonstrated to be efficacious in clinical practice. In a preliminary study, we demonstrated that urinary [TIMP-2]*[IGFBP7] levels 4 hours after CPB showed good performance in predicting the development of AKI (AUC 0.81). Moreover, patients with a cut-off value ≥ 0.3 ((ng/ml)²/1000) were identified to have a high risk for AKI (5-times higher than [TIMP-2]*[IGFBP7] < 0.3; p< 0.001). Thus, preventing AKI after cardiac surgery would have a great impact on morbidity and mortality.

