4.7 Efficacy and safety variables

4.7.1 Measurement of efficacy and safety variables

- 4.7.1.1 Primary target variable
 - Compliance rate (proportion of patients who are treated according to the trial protocol):
 KDIGO recommendations fulfilled at all time
- 4.7.1.2 Secondaryand other target variables
- Occurrence of AKI within the first 72 hours after cardiac surgery (AKI will be defined according to the KDIGO guidelines)
- Moderate and severe AKI within 72 hrs (according to the KDIGO guidelines)
- Severity of AKI within 72 hrs
- Renal recovery

Renal recovery at hospital discharge and at days 30, 60 and 90 will be defined asserum creatinine levels < 0.5 mg/dl higher than baseline.

- 30-day, 60.day and 90-day mortality
- Length of stay in intensive care unit and hospital

CONFIDENTIAL

Date: 16.02.2017 Version: V1

Information on ICU and hospital stays will be documented. From admission to ICU admission until follow-up (by phone) at day 90, the location of the patient within the hospital will be documented in the CRF. The following will be recorded for each patient

- Date and time of admission to ICU
- Date and time of discharge from ICU
- Date and time of discharge from hospital
- Need and duration of RRT during hospital stay
- RRT at days 30, 60 and 90
- MAKE₃₀, MAKE₆₀ and MAKE₉₀ (major adverse kidney events consisting of mortality, dialysis dependency persistent renal dysfunction (defined as serum creatinine ≥ 2x compared to baseline value)
- Determination of different biomarkers

Blood and urine samples for biomarkers will be collected at the time of randomization and 12 hrs later

 Assessment of complications related to the implementation of the KDIGO guidelines will be documented.

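### Bundle-related complications are a promised safety outcome, but the schedule names no glucose, fluid-overload or arrhythmia item and section 6.3 gives no safety comparison

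*Combined protocol and SAP*

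**What the plan says.** **The promise.** The synopsis, under study endpoints, says that "complications in particular those related to the implementation of the KDIGO guidelines will be" documented. Section 4.7.1.2 repeats it as an item of its own: "Assessment of complications related to the implementation of the KDIGO guidelines will be documented". Section 5.2.1 counts documenting and reporting such complications among the GCP principles to be followed.

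**The schedule.** The complications row of the visit table in section 4.7.1.3 reads "Complications (myocardial infarction, cerebral ischemia, ICB, bleeding >300ml/hour, re-operation". The laboratory row reads "Laboratory parameter (lactate, hemoglobin, electrolytes". The medication row names vasopressors, contrast agents, diuretics, ACE inhibitors and ARBs; it does not name insulin.

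**The no-harm statements.** Section 4.2: "The KDIGO recommendations are safe and have no side effects". Section 1: "No side effects are expected by implementing the KDIGO guidelines". Synopsis: "No side effects have been reported". Section 5.2 adds that no side effects are known and that neither arm faces extra risk. Section 2.2, however, cites trials in which "strict glucose control might not only be associated with higher AKI incidence but also with higher mortality rates".

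**The analysis.** Section 6.1 leaves safety out of its endpoint list. Section 6.3 gives generic tests for secondary endpoints and does not mention complications.

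**The concern.** The intervention acts on glucose, volume status and hemodynamics. The itemized complications are those of any cardiac-surgery cohort, and none is distinctive of a bundle component. A safety outcome without event definitions, without items matched to the intervention and without a planned comparison depends on someone noticing an event, linking it to the bundle and writing it down. The protocol also says in several places that there is nothing to find.

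This pilot is meant to prepare a large randomized trial. If its report says that no bundle-related complications were seen, the planners of that trial may take this as a safety finding when it may only reflect how the data were collected.

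**Working it through.** **1. The plan's own figure.** The only precision calculation is for the primary endpoint: Clopper-Pearson, 140 of 280, stated as 44% to 56%. Recomputed from beta quantiles it is 43.99% to 56.01%, so it reproduces. There is no corresponding figure for safety.

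**2. Bundle components (section 4.6.1) set against the named variables (section 4.7.1.3 and Appendix 11.3).**
- *Glucose, closely monitored for 72 hours after surgery.* Glucose is not in the laboratory row, insulin is not in the medication row, and hypoglycemia is not a complication item. Neither SOFA nor APACHE II, as tabulated in the appendix, contains glucose. Hypoglycemia cannot be derived from any named variable.
- *Volume and hemodynamic optimization by algorithm.* Fluid balance is scheduled at every visit, and MAP, heart rate, CVP, CI and CO at T2. Respiratory parameters are scheduled at T1 and T2. SOFA carries PaO2/FiO2, MAP and catecholamine bands; APACHE II carries heart rate, MAP and oxygenation. Fluid overload or impaired oxygenation could therefore show indirectly, but no variable is designated as a safety outcome. Pulmonary edema and arrhythmia are not named.
- *Stopping ACE inhibitors and ARBs for 48 hours.* Use of these drugs is recorded; no associated event is named.

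**3. Attribution under blinding.** Section 4.2.2 blinds the investigators who obtain and document data, and the endpoint committee. Someone who does not know the arm cannot reliably judge whether an event is bundle-related. The staff who deliver the bundle do know the arm, but they are kept out of endpoint assessment, and the intervention period ends at 12 hours while the glucose item runs to 72. Reports from them would also tend to come from one arm only. Recording the same predefined events in both arms, without asking about cause, avoids both problems.

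**4. What systematic capture would give.** Input: 140 patients per arm (synopsis).
- Upper limit with no events, two-sided 95%: 1 − 0.025^(1/140) = 0.0260, or 2.6%. One-sided 95%: 1 − 0.05^(1/140) = 0.0212, or 2.1%.
- Chance of at least one event, 1 − (1 − r)^140. The rates r are assumptions; the documents give none:
  - r = 1%: 0.755 (140 × 0.01 = 1.4 expected)
  - r = 2%: 0.941 (2.8 expected)
  - r = 5%: 0.999 (7 expected)
- Power of a between-arm comparison, 140 per arm, two-sided 5%, again at assumed rates: 35% for 5% versus 10%, 64% for 2% versus 8%, 80% for 5% versus 15%.

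At these rates, events would probably occur and could be counted, but only large differences would be detected. This argues for estimates with intervals rather than reliance on tests.

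**The case against.** The strongest reply is that the protocol does look for harm. Documentation of bundle-related complications is promised openly and is not limited to the five events in the table. A hypoglycemic episode or pulmonary edema judged to be due to the bundle would have to be documented by anyone following the text. Fluid balance, hemodynamics, organ-failure scores, vasopressors, RRT and mortality are collected in both arms, and mortality is compared as a secondary endpoint. Infarction, cerebral ischemia and bleeding could plausibly be affected by fluid and hemodynamic management, and in a randomized comparison an excess is informative whether or not the event is unique to the bundle. Because the synopsis lists safety among the secondary endpoints, the generic tests of section 6.3 might be read as covering it.

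Most of this stands. A reader might infer that the trial never looks for bundle harm, or that its safety result is zero by construction. The documents do not support either reading.

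What the reply does not repair is the missing definition, the attribution problem under blinding, and the glucose gap. Judging compliance may require some glucose recording, but the schedule names none, and a check for high values need not yield the lowest value. Whether section 6.3 covers complications is left unclear, since section 6.1 omits them.

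A reader might also infer that section 2.2 flatly contradicts the no-harm statements. That is too strong: the cited evidence concerns strict glucose control, the bundle calls for avoiding hyperglycemia, and the visible text gives no glucose target. The two are in tension, and strict control is neither prescribed nor excluded.

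**Conclusion.** The point holds in a limited form. The promised bundle-specific safety assessment has no event definitions, no glucose or hypoglycemia item, no designated item for fluid overload, pulmonary edema or arrhythmia, and no stated comparison by arm. An absence of reported bundle harm would therefore be weak evidence of safety. It would not be meaningless, because indirect signals are collected.

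The size of the loss is modest but real. With systematic capture, 0/140 would bound a harm at about 2.6%; without it, even that bound cannot be claimed. The bound assumes 140 analyzed intervention patients and complete ascertainment; the event rates and powers in the working are illustrative assumptions.

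Two limits apply. Figure 1 is not shown, so the drugs and fluids in the algorithm cannot be checked, and the case for an arrhythmia item is weaker than that for glucose. The subsections before 3.5 and the appendix material before 11.3 were not available. The primary endpoint and the sample size are unaffected. The change should be made because it alters what the trial can conclude about safety.

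**What to change.** 1. **Data.** Add to the eCRF, for T2 to T5 in both arms and regardless of presumed cause: blood glucose including the lowest value, hypoglycemia, pulmonary edema or fluid overload, and new arrhythmia. The clinical team should write the event definitions before enrollment starts.
2. **Analysis.** Add safety to section 6.1. In section 6.3, state that these events and the existing complications row will be reported as counts and proportions by arm with exact (Clopper-Pearson) confidence intervals, and that the trial is not powered to exclude moderate differences.
3. **Wording.** Reconcile the no-harm statements with the evidence cited in section 2.2. They differ and need separate edits: section 4.2 asserts safety outright, section 5.2 denies any extra risk, section 1 expects no side effects and the synopsis says none have been reported. The text should also make clear how the glucose component relates to the strict control discussed in section 2.2.

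The cost is a few eCRF fields at four visits, assumed to be available from routine charts, plus text edits. Treatment, sample size and the primary analysis do not change. The downside is slightly more data entry.

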4.8 Documentation

All data relevant to the trial are documented soon after measurement by the responsible investigator in the electronic case report form (eCRF) supplied. Entering data may be delegated to members of the trial team.

The information technology (IT) infrastructure and data management staff will be supplied by the ESICM Trials Group in cooperation with the Department of Anesthesiology, Intensive Care and Pain Medicine, University Hospital Muenster. The trial database will be developed and validated before data entry based on standard operating procedures (SOPs). The database that will be used is CLINFILE(© and is integrated into a general IT infrastructure and safety concept that complies with ICH E6 Standard, ISO 14155 standard, FDA 21 CRF Part 11 and Eudralex Annex 11.with a firewall and backup system. The data are backed up every hour in RAID 10 (disk cloning). After completion and cleaning of data, the database is locked and the data exported for statistical analysis.

4.8.1 Archiving

All CRFs, informed consent forms and other important trial materials will be archived for at least 10 years at each trial site.

CONFIDENTIAL

Date: 16.02.2017 Version: V1

5 Ethical and regulatory aspects

5.1 Independent ethics committee

The clinical trial will not be started before approval of the competent ethics committee. The principal investigator will inform the ethics committee about any changes in the study protocol.

5.2 Ethical basis for the clinical trial – Risk/benefit ratio

The present trial protocol and any amendments were and will be prepared in accordance with the Declaration of Helsinki in the version of October 2013 (64th General Assembly of the World Medical Association, Fortaleza, Brazil).

All patients will receive standard perioperative care. No side effects of the implementation of the KDIGO guidelinesare known. None of the patients in both groups will be exposed to additional risks.

AKI after cardiac surgery is associated with an increased morbidity and mortality. Despite numerous clinical trials of pharmacologic interventions, a mean to prevent AKI associated with cardiac surgery has remained elusive. In a preliminary study, we demonstrated that urinary [TIMP-2]*[IGFBP7] levels 4h after CPB showed a good performance in predicting the development of AKI (AUC 0.81). Moreover, patients with a cut-off value ≥ 0.3 ((ng/ml)²/1000) were identified as patients with a high risk for AKI (5-times higher than [TIMP-2]*[IGFBP7] < 0.3; p< 0.001). Thus, preventing AKI after cardiac surgery would have a great impact on morbidity and mortality.

Participation in this study will be voluntary. Written informed consent will be obtained from patients. If the patient is unable to provide informed consent, local regulations provided by the competent, country-specific local ethics committee with respect to patients without capacity to consent, have to be followed. Independent of the opt-in process of the corresponding ethics committee, informed consent of the patient or legally authorized representative will be obtained as soon as the patient's condition allows it.

Data collection will be performed pseudo-anonymously and the patient's name will not appear on any CRF or in any other trial document submitted to the central data management. All collected data will be kept confidential.

The treating investigator will inform the patient or the legal representative in case the patient lacks capacity about the nature of the trial, its aims, expected advantages as well as possible risks. Each patient must consent in writing to participate in the study. The patientand legal

CONFIDENTIAL

Date: 16.02.2017 Version: V1

representative must be given enough time and opportunity to decide whether to participate and to ask questions before the beginning of documentation of the study.

The informed consent forms will be signed by both patient or legal representative and investigator. The original document is kept by the investigator and the patient receives a copy.

